Summary of revisions made: Amendment 12; 1) Changes to risk: All surveys will be screened upon receipt by study staff. If a psychiatric emergency is reported on surveys (i.e., expression of risk for suicide or homicide), a number of steps will be taken. The patient's treating clinician will be notified and the disclosing participant will be contacted by phone, assessed for risk and safety, and provided with appropriate referrals. We anticipate in this population of participants that indications of suicidality and homicidality are chronic, common, and known to the clinician team. Specifically, study staff will check the final item of the PHQ-9 on all returned surveys. Staff will also read any text written into the survey for any concerns that the participant may be at risk to harm themselves or others or may be at risk to be harmed by someone else. In cases of low severity (subject endorsed "1" on PHQ-9), study staff will immediately notify the treating clinician and indicate that they can follow-up with the patient as clinically indicated. For more severe cases (subject endorsed a "2" or "3" on PHQ-9), a trained staff member will immediately reach out to the participant and assess them for risk and safety and provide them with appropriate resources. Staff will then notify the patient's treating clinician to inform them of the situation. 2) Modified the letters sent in the mail with study surveys to state "If you would like to discuss any of your survey responses further with a study staff member, please call." 3) Added a more precise item to more accurately identify those who need outreach after study surveys, which would help optimize the amount of outreach effort done by site PIs (when no VA MH provider is assigned or available). Add the two questions used in CSP 591 (comparative effectiveness trial comparing two psychotherapies for PTSD) to assess suicidal ideation; adapted from the Linehan BRTC SI screen.

Version number 14

Version date: June 8, 2020

Summary of revisions made: Amendment 13; 1) Added use of Qualtrics FedRAMP electronic survey for study surveys. 2) Added correspondence with study participants using email usage. 3) Added correspondence with study participants using VA cell phone, personal cell phone, or Doximity when study staff are teleworking. 4) Added use of alternative forms of VVC (formats approved by the VA). 5) Requiring patients be seen via telehealth when in-person treatment isn't available.

Version number 15

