
When staff interact with participants over the phone and wish to transfer a participant to the National Suicide Prevention hotline, it is possible, albeit unlikely, that the patient will decline the transfer or hang up. This refusal to be transferred does not necessarily mean the patient is immediate danger of suicide. We consulted with the hub site's Suicide Prevention Program Coordinator on how to respond in this scenario ([name]). [name] recommended the following: (1) If the staff member is able to determine that the patient is not in immediate danger for suicide (e.g., "Are you certain you are safe today?"), then staff member should express his/her care and concern, encourage help seeking, provide the patient with the national suicide hotline number and local MH phone number(s), and respect his/her wishes not to be transferred. (2) If the staff member is concerned the participant may be in immediate danger, he/she will contact local police and initiate a well-check if the participant is unwilling to be transferred. (3) If the staff member does not have enough information to determine if the participant is in immediate danger, he/she will immediately consult with the site PI (each of whom are clinical psychologists) or another MH provider among the study staff, whomever the staff member is able to reach first. This is most likely under scenarios in which the participant hangs up on the staff member and failed to respond to the staff members efforts to call him/her back.

The final phase of our suicide management protocol is *Documentation*. Staff will report use of the suicide management protocol within the same day to the site's study coordinator and site principal investigator. For veteran participants who receive their care at that study site, use of the protocol will be documented in the

patient's electronic medical record. This will also be done for VA patients not enrolled in the study (e.g., when interactions happened during recruitment). If the participant has a VA mental health provider, this individual will be notified by co-signing the provider on the CPRS note (their MH provider, or if no MH provider their PCP) using the use the CPRS Action "Identify Additional Signers". Lastly, this will be recorded in study records as an adverse event and in an excel document for the study that documents all the steps taken in response to the participant's expressed suicidal ideation.

Figure 1. Suicide Management Protocol

[figure not shown]

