Reports of risk on study surveys. All surveys will be screened within 2 business days of receipt by study staff. This will ensure that surveys are typically screened within 48 hours of receipt by a study staff, barring holidays and weekends (e.g., staff has until Tuesday to screen a survey received on Friday). Staff will read any text written into the survey for any risk-related concerns, as well as review responses to the adapted Linehan BRTC SI screen items that directly assess suicidal ideation. Staff will be carefully trained about the importance of opening surveys promptly and entering receipt of each survey into the study tracking application. Auditing will be performed quarterly to ensure that the staff member reviewed the participants responses on Linehan BRTC SI screen items and intervened appropriately when the final item response was greater than "5".

If any psychiatric emergency is reported on surveys (i.e., expression of risk for suicide or homicide) or a response of greater than "5" on Linehan BRTC SI screen items, the participant's VA Mental Health Provider will be notified using phone, skype, and pager. If the participant does not have a VA Mental Health Provider or their VA Mental Health Provider is unavailable (we are not able to reach the provider within the same business day), a study designated MH provider would do the necessary outreach. There are a number of licensed MH providers on the study team. Some are clinically privileged and others are not clinically privileged (e.g., Research Service employees). When providers are not privileged, we propose they will utilize the C-SSRS screener as outlined in the study protocol (see "Suicide Management Protocol"). When providers are privileged, we propose they use either the C-SSRS screener protocol or a more stringent approach to suicide risk assessment that is consistent with VA guidelines.

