6.0 Reporting

We will follow the VA Central IRB Table of Reporting Requirements for all issues that must be reported (i.e. summary of adverse events, unexpected problems and any actions or changes with respect to the protocol).

Adverse events (AE) include any untoward medical occurrence in a patient or clinical investigation subject administered an intervention and which does not necessarily have a causal relationship with this treatment. We will collect the following safety information (adverse events) that occurred within 7 days leading up to the final assessment.

1. Suicide attempts
2. Hospitalizations for mental health
3. Episodes of family violence

Therapists will be instructed to notify study staff immediately when such events occur during treatment delivery. Staff will report directly to the local site PI regarding any events. Counselors will also meet regularly by phone for case consultation with a study investigator, where the occurrence of any of these events will be further discussed and tracked. Questions regarding the occurrence of each of these three events will be included in posttreatment assessments. Data obtained from participants will be reviewed for safety concerns. In the case of problems, the staff will discuss this with the appropriate site PI.

Of note, survey reports of IPV on posttreatment and follow-up surveys will be reported when respondents endorse items consistent with severe violence. This includes the following: (1) hit my partner with a fist or something hard, (2) kicked my partner, (3) slammed my partner against something, (4) beat my partner, (5) burned my partner on purpose, (6) tried to hurt my partner by choking or suffocating him/her, or (7) used a knife or gun on my partner. Examples of serious adverse effects, according to the FDA, include death, life-threatening adverse events, suicide attempts, and hospitalization. Consequently, endorsement of items 6 or 7 will be considered a SAE. Given the population, some incidents of severe IPV are expected. Reports of severe IPV on baseline surveys are part of our exclusionary criteria (see inclusions/exclusions). Thus, severe IPV in reported in baseline surveys will not be reported as adverse events.

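### The quarterly audit of survey-reported risk checks intervention only for the final suicide-screen item, which is narrower than the action rule it is meant to verify

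*Combined protocol and SAP*

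**What the plan says.** All of the operative text is in section 5.1K.1, under *Reports of risk on study surveys*.

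- **Reading duty.** Besides looking at the suicidal-ideation screen items: "Staff will read any text written into the survey for any risk-related concerns".
- **Action rule.** The rule opens "If any psychiatric emergency is reported on surveys (i.e., expression of risk for suicide or homicide) or a response of greater than" 5 and continues "on Linehan BRTC SI screen items, the participant's VA Mental Health Provider will be notified using phone, skype, and pager". If there is no such provider, or the provider cannot be reached that business day, a study mental health provider makes the contact.
- **Audit, first part.** "Auditing will be performed quarterly to ensure that the staff member reviewed the participants responses on Linehan BRTC SI screen items".
- **Audit, second part.** The audit also establishes that staff "intervened appropriately when the final item response was greater than" 5.

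The Amendment 12 revision summary, used here only as context, introduced the screen with the words "Add the two questions used in CSP 591". The screen therefore appears to have two questions, so the final item is only one of them.

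**The concern.** The action rule and the audit's intervention check sit in the same section but do not cover the same surveys. The rule applies to the screen items in the plural and to any expression of suicide or homicide risk. The intervention check applies to one item. An auditor who followed the sentence exactly could record a pass for a survey on which a required response was never made.

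The audit is the only check the documents describe specifically for how staff respond to risk reported on surveys. Homicide risk is named in the action rule but not in the audit. Some respondents also have little other contact through which a miss might be noticed. Section 5.1K.1 says support persons in standard PE are never treated as actively engaged in study psychotherapy, and section 5.1 plans 78 of them. What is at stake is safety oversight; no estimate or test is affected.

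**Working it through.** The plan gives no figure to reproduce. The check compares what the action rule requires with what the audit sentence names, trigger by trigger.

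| Trigger on a returned survey | Response required? | Review audited? | Intervention audited? |
|---|---|---|---|
| Final screen item above 5 | Yes | Yes | Yes |
| Earlier screen item above 5 (if its scale allows) | Yes | Yes | No |
| Suicide or homicide risk expressed elsewhere on the survey | Yes | Not named | Not named |
| Written text expressing such risk | Yes, as a reported emergency | Not named | Not named |

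Written text is not a separately listed trigger. Staff must read it, and it leads to action through the psychiatric-emergency limb of the rule.

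**Does another section close the gap?**

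- The documentation phase of the suicide management protocol (section 5.1K.1) says: "Staff will report use of the suicide management protocol within the same day to the site's study coordinator and site principal investigator". That records use of the protocol. An omitted response creates no such record.
- Section 6.0 says: "Data obtained from participants will be reviewed for safety concerns". That is a general review of data and does not check whether staff acted on a particular survey.
- Section 5.1K.1 has study therapists review answers on partner violence during active therapy. It says nothing equivalent for the suicide screen.

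No other section describes an audit of these responses.

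**Scale.** Sections 5.4E and 5.5A.3 schedule, for each randomized Veteran and support person, 1 baseline + 7 weekly + 1 posttreatment + 1 three-month survey = 10. Section 5.1 plans 156 + 156 = 312 randomized participants, so 10 × 312 = 3,120 surveys are due. The count leaves out baseline surveys from dyads enrolled but not randomized (225 − 156 = 69 dyads planned), intensive-coaching surveys and baseline retakes. The documents do not say which surveys carry the screen items, or how often an earlier item or an expression of risk elsewhere is the only trigger. No rate of missed responses can be derived.

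**The case against.** The strongest reply is that there is one action rule, it is complete, and the other sentence only describes an audit. A reader might infer that staff are given two competing triggers and that sites will work to the narrower one. The documents do not support that. The duty to respond is stated once, staff are trained and supervised by a licensed psychologist on a structured protocol, and section 5.1K.1 lets sites be more stringent than its minimum. The mismatch lies in what is verified.

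A reader might also infer that the audit ignores every survey whose trigger is not the final item. That goes too far as well: review of all screen items is audited, and for an earlier item only the intervention check is missing.

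The item-level gap also depends on an instrument that is not in the documents. If only the final question can be answered above 5, the two wordings pick out the same responses and that part of the gap closes. The phrase may be left over from the procedure in the Amendment 12 summary that used the last PHQ-9 item. That is an inference, and it would explain the wording without changing what the current text tells an auditor to check.

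Finally, a miss need not stay hidden. Weekly consultation calls (section 5.1G), and therapist notification and posttreatment questions about suicide attempts, psychiatric hospitalizations and family violence (section 6.0), could bring one to light. This is fair, and it rules out saying that a miss would never be found. None of these routes checks whether staff responded to a given survey, so the gap in the audit itself remains.

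**Conclusion.** The concern holds as a coverage gap in one safety check. Followed exactly as written, the audit could pass a survey on which a response required by the protocol was not made. For emergencies expressed elsewhere on the survey or in text, this rests only on the current wording. For an earlier screen item, it also assumes that the item's scale can exceed 5.

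The size cannot be quantified. A reader might take the 3,120 surveys as a measure of missed responses or of unaudited surveys. It is neither, only a rough count of what is due from randomized dyads. Outcomes, randomization, power and analysis are unaffected. The point is more than a typographical slip because an auditor would act on the sentence, and it is cheap to correct. No view is taken here on which threshold or trigger is clinically right.

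**What to change.** Reconcile the action and audit sentences in section 5.1K.1, with the clinical investigators deciding the trigger wording. The audit's intervention check should then use the same trigger definition as the action rule, and should include surveys with a reported emergency or risk-related text as well as those above the screen threshold. If rereading all written entries is too much, check text on a sample of surveys each quarter and state how the sample is drawn. If the investigators confirm that only the final item can exceed 5, saying so would settle the item-level part.

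The cost is a change to two sentences and a somewhat larger quarterly audit, with most of the extra work in checking text. No new data are collected from participants.

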5.2 Recruitment Methods

5.2A. Study Settings and Recruitment.

Data collection will take place at three sites, including the Minneapolis, Atlanta, and Ann Arbor VA Health Care Systems. All three sites deliver a high volume of PE and provide an ideal environment for this work. We approached a number of sites delivering a high-volume PE, identified from an ongoing study conducted by Drs. [name] and [name]. We then selected sites with a strong research culture, history of clinical trials of PTSD treatments, existing structure for recruiting and conducting trials for Veterans with PTSD, and a large number of trained PE providers (n = 57, across sites). The study will be based in the Center for Chronic Disease Outcomes Research (CCDOR). Atlanta's and Ann Arbor's Site PIs each have experience conducting RCTs with Veterans with PTSD and were actively involved in study development.

5.2B. Veteran Recruitment

Given the importance of recruitment to the success of any study, we plan to rigorously train all staff in established best-methods for recruiting for behavioral intervention trials (e.g., Leonard, Lester, Rotheram-Borus, Mattes, Gwadz, & Ferns, 2003).¹⁰⁶ Training will address how to handle difficult situations while maintaining boundaries, establish and maintain rapport while not antagonizing or alienating participants, and handling reports of IPV or other risk issues. Methods will include role-play of challenging situations (e.g., reluctance to continue an interview as a family member enters the room, multiple phone interruptions, and requests participants may make that are outside the scope of the interview protocol, such as an additional stipend or loan from the interviewer). It will also include regular recruitment supervision meetings where team members share successful tips from prior studies or experiences within the current study, led by study investigators and staff with backgrounds in clinical and counseling psychology (e.g., Study Manager and all site PIs). Given the importance of establishing rapport to successful participant recruitment¹⁰⁷ and plans for careful training and supervision, staff will be trained in the use of scripts as guides to avoid impersonal or alienating recitation of scripts. Reading scripts verbatim may interfere with establishing rapport, adaptive social norms that promote asking questions, and a safe environment for individuals share when they do not understand or have concerns about the study. See Study Materials for example scripts.

5.2B.1. Referral Sources. We will rely on three methods of identifying potentially eligible Veterans for both the IC and RCT phases of the study: 1) provider referral, 2) self-referral, and 3) identification from hospital records.

Provider Referral. Provider referral will provide our first-line recruitment source, as this will mirror how the intervention is delivered in typical clinic care. We will make announcements about the study in multiple settings and forums (e.g., announcements at team meetings, presentations at grand rounds). We will provide flyers and brochures to providers and discuss the study with them to inform them about the study. As providers and patients may prefer to discuss the study together, prior to referring the patient to our team, fliers and brochures will assist in these efforts. Providers may or may not choose to discuss the study with the Veteran first. We will then receive contact information for potentially eligible patients (i.e., those seeking PTSD care or trauma-focused treatments) by (1) providers or by (2) team-leads in specialty clinics notifying study staff as patients are referred for evidence

based PTSD treatment. Study staff will be provided with patients' contact information through secure email, verbally, or through a cosigned CPRS note that an individual is interested in trauma-focused care (with subsequent communication verbally or through secure messaging).

Self-Referral. To facilitate self-referral, we will use study fliers and brochures strategically placed in appropriate clinic locations and make announcements to inform others about the study. We will also distribute fliers and brochures, make announcements, and provide presentations to community organizations to facilitate self-referral. Individuals who are self-referred to the study will reach out to study staff to express their interest directly.

Identification from Hospital Records. If approaches self and provider referral prove insufficient to reach recruitment goals, we will identify potentially eligible Veterans who have a diagnosis of PTSD through an administrative data pull and recruit these Veterans through the mail and telephone, using the same methods employed for provider referral participants.

5.2B.2. Recruitment Processes: RCT

Provider Referral. Step 1. If the referral source chooses, they can provide Veterans with a study brochure and ask the Veteran if he/she wants to be called about the research study. This will give Veterans an opt out option. If a Veteran responds "no", clinic staff will not contact study staff members. If a Veteran responds "yes", and would like to be called regarding a research study, the provider/staff will notify study staff. Off-team individuals will not make any efforts to recruit the Veteran and will refer the Veteran to study staff with any questions. Alternatively, Veterans' who have not been asked if study staff can contact them will receive a letter in the mail and brochure about the study, informing them they will be contacted and how to decline study recruitment efforts.

Prior to initiating contact with the Veteran, study staff will review hospital records to determine the presence of any study exclusionary criteria (e.g., the patient is currently hospitalized for a psychiatric emergency or reporting active psychotic symptoms).

Step 2. Veterans will then be contacted by telephone and/or in person (i.e., within Mental Health Clinics) by a trained interviewer to discuss the study and for initial screening. In person contacts will only be conducted for Veterans who have already expressed an interest in participating to their provider or to study staff in telephone recruitment efforts. Prior to direct recruitment, all individuals will be mailed a letter describing the study and how to opt out, as well as a study brochure.

In most cases, we expect that provider referrals will come from patients actively seeking mental health care. When a provider or off-team staff member refers a Veteran to study staff without first asking them if they would like to be called regarding a research study, we will send them a study letter and brochure and wait 7 days prior to efforts to reach them. If, upon contact, the individual has not received their study letter, we will offer to contact the individual again at a later date and to re-mail the recruitment letter. When a provider or off-team staff member refers a Veteran who has expressed an interest in being called regarding a research study, study staff will call the Veteran as soon as possible to give them information about the study and for initial screening. This eliminates a delay in getting Veterans into care, and follows the current clinic mandates regarding minimum wait times for evidence based treatment for PTSD. When Veterans referred through providers are deemed ineligible, we will notify their referring provider and refer Veterans back to their mental health care provider.

We will make up to 3 calls a week for 3 weeks, unless the Veteran declines recruitment or requests an alternative schedule (e.g., if he/she asks us to call more often to try to catch them at a time when they aren't busy or are somewhere in private). We will leave up to one

message per week, unless the Veteran requests no voicemails or requests an alternative schedule. See Materials for an example voicemail script.

Step 3. Upon contact with the Veteran, with their permission, a trained interviewer will then discuss the study and complete an initial screening, including for the presence of an eligible SP (see Table 4), willingness to include a SP in at least one session of PE, and presence of moderate intimate partner violence (SF CTS-2), and presence of symptoms of PTSD on the PC-PTSD-5 (see inclusion/exclusion criteria for further detail). When the veteran's baseline surveys are received prior to their structured clinical interview for inclusions/exclusions (described below), we will also review their PCL-5 scores for the presence of symptoms of PTSD. Veterans with a PCL of 27 or lower will be screened out and will not be scheduled for structured clinical interviews.

Level of relationship satisfaction and distress will be assessed through a single item from the Couples Satisfaction Index (CSI-1) and the Interpersonal Stressors Scale of the Life Stressors and Social Resources Inventory (see appendix with Study Materials) in order to compare differences in relationship strain between those who ultimately do and do not enroll. The study procedures (assessment data gathering, intervention, session recording) and study design (including the nature of randomization to condition) will be fully described to the participant at the time of the initial contact (and again at the time that consent is documented). See script for initial screening call in Materials. For interested and eligible Veterans, we will begin recruitment efforts for their SPs and begin or schedule the over-the-phone informed consent meeting with the Veteran to complete enrollment.

For Veterans who have expressed interest in the study (i.e., study staff spoke with them over the phone, Veteran completed screener, and/or Veteran completed informed consent), if at any time during the recruitment process study staff are unable to reach them, we will send them one final letter. The letter will inform the participant that we have been unable to reach them and that without contact within 2 weeks, we will have to close their case from our study records. The letter informs the Veteran that we will no longer attempt to contact them, and gives them the opportunity to reach out to study staff if they still have interest in participation in the study.

Self-referral and Referral through Identification from Hospital Records. Procedures will follow the same general process as above with a few exceptions. For self-referrals, these individuals will be contacting study staff first, so we will immediately initiate efforts to return their calls while also sending them an introductory letter and study brochure. See Materials for Introductory Letter.

For patients identified through hospital records, the volume of mailings anticipated makes individual review of patients' records prior to their initial mailing impractical, so this component of the process will not take place prior to mailing for Veterans referred through this channel. Additionally, as these individuals are not necessarily seeking treatment, we will wait 7 days after the initial mailing before attempting to contact them by telephone.

5.2B.3. Recruitment Processes: IC Phase

Provider Referral. All participants for this phase will be identified through provider referral as described above with some exceptions. The difference between IC participants and participants for the randomized controlled trial are (1) providers will receive personalized feedback on every family-supported PE session for these cases (sessions 1, 2a, and 2b) based on review of the audio tape, (2) data will not be used at part of the RCT, since participants are not randomized. As data will not be used for the RCT, we will establish inclusion/exclusion criteria using methods consistent with how this intervention would likely be delivered in routine care (i.e., hospital record review and self-report). These methods are not based on the rigorous gold-standard assessment instruments required for the larger RCT.

Step 1. Hospital records will be reviewed to determine the presence of study exclusionary criteria (e.g., the patient is currently hospitalized for a psychiatric emergency, actively suicidal/homicidal, or reporting active psychotic symptoms, manic symptoms, or severe substance use). Providers who have consented to the study may discuss the study with patients they identify. If interested, providers will ask (1) patient's permission for study staff to call them and ask about (2) the presence of an eligible SP (see Table 4), (3) willingness to include a SP in at least one session of PE, and (4) the presence of moderate intimate partner violence (SF CTS-2; See IC Veteran Self-Report Form in Materials). These changes from the RCT are done for efficiency of recruitment and, due to the small volume of cases in the IC phase are feasible to ask of study providers for this phase of the study. Providers and staff who are not on the study team may provide Veteran patients with a study brochure and ask Veterans if they want to be called about the research study. This will give Veterans an opt out option. If a Veteran responds "no", clinic staff will not contact study staff members. If a Veteran responds "yes", and would like to be called regarding a research study, the provider/staff will notify study staff by encrypted email or through a co-signature on a clinic note in CPRS. Off-team individuals will not make any efforts to recruit the Veteran and will refer the Veteran to study staff with any questions.

If Veterans were not asked if the study could contact them prior to study referral (e.g., provider or an off-team staff did not ask them if they would be willing to be called regarding a research study), Veterans will be sent a letter and brochure describing the study, informing them they will be contacted and how to decline study recruitment efforts. Clinicians will continue to provide study staff with patients' contact information through secure email, verbally, or through a cosigned CPRS note that an individual is interested in trauma-focused care (with subsequent communication verbally or through secure messaging).

Step 2. Veterans will then be contacted by telephone and/or in person (e.g., coordinating with other medical appointments) by a trained interviewer to discuss the study. As with the RCT, for those requiring a pre-notice letter, we will wait 7 days prior to efforts to reach participants. If, upon contact, the individual has not received their study letter, we will offer to contact the individual again at a later date and to re-mail the recruitment letter. For those whose provider obtained permission for staff to contact them and who completed the brief self-report form, Veterans can begin or be scheduled for an informed consent meeting to complete final enrollment.

As with the RCT, we will make up to 3 calls a week for 3 weeks, unless the Veteran declines recruitment or requests an alternative schedule (e.g., if he/she asks us to call more often to try to catch them at a time when they aren't busy or are somewhere in private). We will leave up to one message per week, unless the Veteran requests no voicemails or requests an alternative schedule. See Materials for an example voicemail script.

Step 3. For those who have not completed initial self-reports with their providers (regarding presence of a SP and IPV), upon reaching the Veteran, with their permission, a trained interviewer will then discuss the study and complete an initial screening, including for the presence of an eligible SP (see Table 4), willingness to include a SP in at least one session of PE, and presence of moderate intimate partner violence (SF CTS-2).

The study procedures (assessment data gathering, intervention, session recording) and study design (including the nature of treatment) will be fully described to the participant at the time of the initial contact (and again at the time that consent is documented). See script for initial screening call in Materials. For interested and eligible Veterans, we will begin recruitment efforts for their SPs and begin or schedule the informed consent meeting with the Veteran to complete enrollment.

5.2C. SP Recruitment: IC and RCT Phases

After receiving Veterans' permission to contact their nominated SPs, the recruitment procedures will be similar for SPs. They will be sent a letter, a brochure describing the study, informing them they will be contacted and how to decline study recruitment efforts. This initial mailing will also include an Information Sheet including all of the components of informed consent to be discussed by telephone. They will be contacted by telephone by a trained interviewer to discuss the study, their interest, and assess the presence of moderate relationship violence on the SF-CTS and screen for PTSD, using the same schedule of contacts used for Veterans, described above. If the SP is unable to speak in private to complete the SF CTS-2 and PTSD screen (see Materials for script), we will offer mailed administration and/or schedule a time to administer the brief measure in private by telephone.

5.2D. Provider recruitment.

When it is time to recruit providers for exit interviews (after completing their treatment cases), we will email them to remind them about the interview. Providers will be able to respond to the e-mail to either opt out of contact for the study or to schedule an interview date and time. If providers do not respond to the e-mail, they will receive a follow-up e-mail and three phone calls from the study team. If we do not reach or hear back from the provider after those contacts, we will assume they are not interested in participating in the interview.

5.2E. MH Leadership recruitment.

Each of the mental health leadership members have also already been approached by the site PIs as part of establishing the feasibility of this study for the grant proposal supporting this project. They will be re-contacted through email and telephone within the 3 months prior to the interview (see 5.3C). In case of attrition, any additional providers will be recruited through email contact by the site PI, followed by a second email, if needed and three follow-up phone calls.

